## 9.5 Safety Analyses

For the safety assessments, the information of adverse events will be described in detail. Count and percentage will be tabulated for the number of patients with AEs, number of total AEs, number of patients with AEs associated to study dosing and intensity. Adverse events will be coded by the Medical Dictionary for Regulatory Activities (MedDRA®) adverse event dictionary. All the AEs will be categorized by each represented Preferred Terms (PT) and System Organ Class (SOC), which will be tabulated by body system with related incidence rates. The clinical laboratory tests and electrocardiogram tests will be analyzed to separate subjects into normal and abnormal categories, with number of subjects and percentage of subjects in each category, and McNemar's test or Fisher's exact test will then be applied to test the changes between each visit.

Protocol: GHLIP-2-001

Study Sponsor: Golden Biotechnology Corporation

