
1.2. Study Rationale

Statins-cholesterol lowering drugs are the first-choice treatments for the primary and secondary prevention of CVD, if the patient still has elevated TG and/or low HDL-C despite intensive lifestyle intervention, and addressing compliance with pharmacotherapy and secondary causes of dyslipidemia, additional lipid-modifying therapy may be considered. Along with the long-term treatment with statins in combination with other hypolipidemic drugs or alone, the safety has drawn a particular attention in clinic, such as the elevation of transaminase and rhabdomyolysis, which have raised an idea of developing the other types of lipid-lowering agents from botanic materials.

The primary hypothesis is that Antroquinonol treatment will be well tolerated and will result in greater lowering of TG at week 12 than placebo in patients with hypercholesterolemia and hyperlipidemia. The primary goal is to determine if Antroquinonol will provide greater TG lowering effect than placebo.

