8. ASSESSMENT OF SAFETY

8.1. Adverse Events (AE)

An adverse event is any untoward or unfavorable medical occurrence in a human subject, including any abnormal sign (for example, abnormal physical exam or laboratory finding), symptom, or disease, temporally associated with the subject's participation in the research, whether or not considered related to the subject's participation in the research.

All AEs including local and systemic reactions not meeting the criteria for "serious adverse events" will be captured on the appropriate AE page of CRF. Information to be collected includes event description, time of onset, clinician's assessment of severity, relationship to study product (assessed only by those with the training and authority to make a diagnosis) and time of resolution/stabilization of the event. All AEs occurring while on study must be documented appropriately regardless of relationship. All AEs will be followed to adequate resolution which means subjects experiencing AEs shall be followed until recovery, recovery with residual effects, continuing, death or lost to follow-up and be recorded on CRF AE page.

Pre-existing conditions will be recorded as baseline on the "Medical History" of CRF. If the pre-existing condition does not change, it does not have to be reported as an AE on subsequent cycles. However, if it deteriorates at any time during the study, it will be recorded as an AE.

All AEs must be graded for **severity** and **relationship** to study product. The adverse event toxicity grading scale used will be the CTCAE v4.03 grading score.

Severity of AEs

All AEs will be assessed by the clinician using a protocol defined grading system. For events not included in the protocol defined grading system, the following guidelines will be used to quantify intensity.

Grade 1	Mild; asymptomatic or mild symptoms; clinical or diagnostic observations only; intervention not indicated.
Grade 2	Moderate; minimal, local or noninvasive intervention indicated; limiting age-appropriate instrumental ADL.
Grade 3	Severe or medically significant but not immediately life-threatening; hospitalization or prolongation of hospitalization indicated; disabling; limiting self care ADL.
Grade 4	Life-threatening consequences; urgent intervention indicated
Grade 5	Death related to AE.

ADL: activities of Daily Living

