9.4. Analysis Plan

General data analysis

For continuous endpoints, descriptive statistics including number, mean, median, standard deviation, minimum, maximum, and 95% confidence intervals will be presented. Continuous variables will be analyzed by means of ANOVA with Bonferroni adjustment. Paired T-Test will be used to compare the change from baseline within treatment groups. If the data strongly indicate a violation of the normal assumption, the non-parametric method of Kruskall Wallis test or Wilcoxon Signed-Rank Test will be applied for analysis.

For categorical endpoints, the count and percentages will be used to summarize the categorical data. The Chi-square test will be performed to test the difference between groups while Fisher's exact test will be applied for any counting of the frequency is less than 5.

All statistical analyses will be conducted using SAS software.

Endpoints

The primary efficacy endpoint for assessing the superiority of Antroquinonol to placebo will be analyzed using analysis of covariance (ANCOVA) model and baseline measurement as covariates, if the differences in baseline characteristics, such as gender, age, weight etc., are observed, for comparing the effectiveness between the treatment groups.

Analysis of other secondary efficacy endpoints (TC, HDL-C, LDL-C, and LDL/HDL ratio as well as the effect of Antroquinonol on E/E', baPWV and ABI and HU parameters) will be similar to the primary analysis of the primary endpoint. All tests will be based on a significance level of 0.05, without adjustment for multiple endpoints.

For the safety assessments, the information of adverse events will be described in detail. Count

and percentage will be tabulated for the number of patients with AEs, number of total AEs, number of patients with AEs associated to study dosing and intensity. Adverse events will be coded by the Medical Dictionary for Regulatory Activities (MedDRA®) adverse event dictionary. All the AEs will be categorized by each represented Preferred Terms (PT) and System Organ Class (SOC), which will be tabulated by body system with related incidence rates. The clinical laboratory tests and electrocardiogram tests will be analyzed to separate subjects into normal and abnormal categories, with number of subjects and percentage of subjects in each category, and McNemar's test or Fisher's exact test will then be applied to test the changes between each visit.

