## 10.2 Clinical Laboratory Evaluations

Descriptive summaries (mean, SD, median, minimum, and maximum for each group with related 95% confidence interval.) of changes from baseline will be presented for clinical laboratory values by treatment for the Safety Population.

The number of patients with clinical laboratory values below, within, or above normal ranges, pre-procedure versus post-procedure will be tabulated for each test, for the Safety Population by treatment group. Pre- and post-procedure values will also be presented with an analysis of mean changes from baseline. Laboratory assessment results will be classified to normal or abnormal, and will be tabulated with related frequency and percentages. The shift tables of laboratory results will also be provided.

Laboratory values that are outside the normal range will also be flagged in the data listings, along with corresponding normal ranges. Any out-of-range values that are identified by the investigator as being clinically significant will also be shown in a data listing.

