### 14.4 Safety Data

Table 14.4.1.1 Summary of Vital Sign by Visit (Safety Population)

Table 14.4.1.2 Summary of Mean Change from Baseline in Vital Sign (Safety Population)

Table 14.4.2.1 Summary of of Physical Examinations (Normal/Abnormal) (Safety Population)

Table 14.4.2.2 Transition Table of Physical Examinations (Safety Population)

Table 14.4.3.1 Summary of baPWV, ABI, E/E', and HU (Safety Population)

Table 14.4.3.2 Summary of of 12-Lead ECG, baPWV, ABI, E/E', and HU (Normal/Abnormal) (Safety Population)

Table 14.4.3.3 Transition Table of 12-Lead ECG, baPWV, ABI, E/E', and HU after 12 Weeks (Safety Population)

Table 14.4.4.1 Summary of Laboratory Assessment-Lipid Profile (Safety Population)

Table 14.4.4.2 Summary of Laboratory Assessment-Serum Chemistry (Safety Population)

Table 14.4.4.3 Summary of Laboratory Assessment-Hematology (Safety Population)

Table 14.4.4.4 Summary of Laboratory Assessment-Biomarkers (Safety Population)

Table 14.4.4.5 Summary of Laboratory Assessment-Urinary Exam (Safety Population)

Table 14.4.5.1 Summary of Laboratory Assessment-Lipid Profile (Normal/Abnormal) (Safety Population)

Table 14.4.5.2 Summary of Laboratory Assessment-Serum Chemistry (Normal/Abnormal) (Safety Population)

Table 14.4.5.3 Summary of Laboratory Assessment-Hematology (Normal/Abnormal) (Safety Population)

Table 14.4.5.4 Summary of Laboratory Assessment-Biomarkers (Normal/Abnormal) (Safety Population)

Table 14.4.5.5 Summary of Laboratory Assessment-Urinary Exam (Normal/Abnormal) (Safety Population)

Table 14.4.5.6 Summary of Laboratory Assessment-Microscopy (Normal/Abnormal) (Safety Population)

Table 14.4.6.1 Transition Table of Laboratory Assessment-Lipid Profile (Safety Population)

Table 14.4.6.2 Transition Table of Laboratory Assessment-Serum Chemistry (Safety Population)

Table 14.4.6.3 Transition Table of Laboratory Assessment-Hematology after 12 Weeks (Safety Population)

Table 14.4.6.4 Transition Table of Laboratory Assessment-Biomarkers after 12 Weeks (Safety Population)

Table 14.4.6.5 Transition Table of Laboratory Assessment-Urinary Exam after 12 Weeks (Safety Population)

Table 14.4.6.6 Transition Table of Laboratory Assessment-Microscopy after 12 Weeks (Safety Population)

Table 14.4.7.1 Summary of Subject Compliance for the Study Drugs (Safety Population)

Table 14.4.8.1 Summary of Adverse Events by Treatment Groups (Safety Population)

Table 14.4.8.2 Summary of Adverse Events by MedDRA Coding (Safety Population)

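### The categorical and tested laboratory analyses cannot show worsening from an abnormal baseline; add a shift table by CTCAE grade or multiple of ULN

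*SAP*

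**What the plan says.** Protocol 9.4 and SAP 9.5 carry the same rule. In the protocol, laboratory and ECG tests are "analyzed to separate subjects into normal and abnormal categories, with number of subjects and percentage of subjects in each category". SAP 9.5 repeats this ("The clinical laboratory tests and electrocardiogram tests will be analyzed to separate subjects into normal and abnormal categories") and, like the protocol, adds that "McNemar's test or Fisher's exact test will then be applied to test the changes between each visit".

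SAP 10.2 contains more than this:

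- Descriptive summaries (mean, SD, median, minimum, maximum, 95% CI) "of changes from baseline will be presented for clinical laboratory values by treatment for the Safety Population".
- A pre- versus post-procedure count of patients below, within or above the normal range. Those two time points are not defined, although chemistry is drawn at several visits.
- A two-category table: "Laboratory assessment results will be classified to normal or abnormal, and will be tabulated with related frequency and percentages".
- Shift tables, with categories not stated.
- Listings that flag every out-of-range value, and a further listing of values judged clinically significant.

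For serum chemistry, SAP 14.4 lists a summary (Table 14.4.4.2), a normal/abnormal table (14.4.5.2) and a transition table (14.4.6.2). Neither document plans a laboratory table by severity grade, multiple of ULN or fold change.

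On adverse events, Protocol 8.1 says: "The adverse event toxicity grading scale used will be the CTCAE v4.03 grading score". It includes abnormal laboratory findings in the adverse event definition and requires worsening of a pre-existing condition to be recorded as an event.

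**The concern.** A two-category scale sees only crossings of the limit. Movement further above the limit is invisible to it, and that is the movement that matters most for liver and muscle safety.

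Patients can start above the limit. Protocol 4.3 sets its hepatic severity limit at Child-Pugh B/C and gives no ALT, AST or CPK threshold. The schedule in Protocol 6.1 first calls for these three tests at Visit 2, the randomization visit; of the chemistry tests, only creatinine is required at screening. Fatty liver is expected often enough to have its own endpoint and a repeat CT scan.

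The trial compares three doses with placebo, and safety against placebo is a stated objective. If patients with raised baseline values worsened with dose, the transition table and its test could report no change in every arm.

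**Working it through.** **The documents give no figure to reproduce.** They state no power, alpha or expected rate for laboratory outcomes, no ULN and no baseline abnormality rate. The check concerns the classification rule. It uses 30 patients per arm (Protocol 9.2) and these assumed ALT values: ULN 40; k patients at 60 at baseline (60/40 = 1.5 × ULN); all others normal and unchanged.

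**Step 1: the categorical test.** McNemar's test uses only discordant pairs: b (normal to abnormal) and c (abnormal to normal). If the k patients rise 2-, 5- or 10-fold, they reach 120, 300 or 600, which is 3, 7.5 or 15 × ULN. Each was abnormal before and is abnormal after. For k = 3, 6 or 9 and any of these rises, b = 0 and c = 0, so b + c = 0 and p = 1. Fisher's exact test also depends only on category counts, and these stay at k abnormal of 30. In the below/within/above table every one of these patients goes from above to above.

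**Step 2: the opposite error.** A patient moving from 0.99 to 1.01 × ULN (39.6 to 40.4) adds 1 to b and is a full event.

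**Step 3: what the change-from-baseline summary shows.** At a 5-fold rise each affected patient changes by 300 − 60 = +240. The arm mean change is k × 240/30:

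| k | Mean change | Median change | Maximum change |
|---|---|---|---|
| 1 | +8 | 0 | +240 |
| 3 | +24 | 0 | +240 |
| 6 | +48 | 0 | +240 |
| 9 | +72 | 0 | +240 |

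So this summary does register the rise, through the mean and the maximum.

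**Step 4: what it does not show.** The maximum is the same whether 1 or 9 patients reached 7.5 × ULN. The mean does not settle the count either. Three patients at +240 give 720/30 = +24. One patient at +240 and eight at +60 (the 2-fold rise) give (240 + 480)/30 = +24. Median (0) and maximum (+240) also agree, yet three patients reached 7.5 × ULN in one case and one in the other. The SDs differ (about 73 against 49), but a reader cannot turn an SD into a count.

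**Step 5: a single patient.** A rise from 1.1 to 10 × ULN moves the arm mean by (10 − 1.1)/30 = 0.30 × ULN. The maximum change in that arm would be 8.9 × ULN.

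**Step 6: how many patients could be affected.** If 20–40% of patients start with abnormal ALT (an assumption; the documents give no rate), that is 0.20 × 30 = 6 to 0.40 × 30 = 12 per arm.

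**The case against.** The strongest reply is that laboratory safety does not rest on the categories alone. SAP 10.2 plans change from baseline by treatment with maximum and 95% CI, and it flags all out-of-range values, not only those an investigator thinks important. No section makes the McNemar or Fisher test the main laboratory comparison, and the protocol summary says laboratory parameters will be reported descriptively. There is also a graded route by arm: a worsening laboratory abnormality can be recorded as an adverse event with a CTCAE grade, and SAP 10.1.1 tabulates events by maximum intensity and treatment group. All of this stands. A reader might infer that a many-fold rise would go unseen in the trial; the documents do not support that.

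A reader might also infer that the protocol names liver and muscle injury as toxicities of the study drug. It does not. The phrase "such as the elevation of transaminase and rhabdomyolysis" in Protocol 1.2 describes statins and other lipid-lowering drugs. For the study drug, Protocol 1.3.1 and 8.2 name diarrhea, vomiting and nausea. The subject is still relevant, because Protocol 1.2 uses those toxicities as motivation for a new agent, Protocol 3.4 makes muscle symptoms a safety endpoint, and AST, ALT and CPK are scheduled at every visit from 2 to 6 in Protocol 6.1.

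Two further replies stand in part. The categories of Table 14.4.6.2 are not stated, so reading it as normal/abnormal or below/within/above is an inference, though these are the only laboratory categories the SAP defines. And investigator discretion at entry may exclude some patients with raised values.

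The reply does not close the gap. The adverse event route depends on an investigator recording an event, listings leave the counting to the reader, and Step 4 shows that mean, median and maximum do not give the count. SAP 14.4 also has no separately titled mean-change table for laboratory values, although it has one for vital signs (14.4.1.2) and for anthropometric measures (14.3.1.2).

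**Conclusion.** The point holds for the categorical and tested laboratory analyses: Protocol 9.4, SAP 9.5, the range and normal/abnormal tables of SAP 10.2, Table 14.4.5.2 and, as far as its categories can be read, Table 14.4.6.2. For a patient above range at baseline they cannot detect further worsening, whatever its size. This follows from the rule itself and needs neither the assumed ALT values nor the 20–40% range.

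The point does not extend to laboratory safety as a whole. Descriptive change, flagged listings and graded adverse events give partial cover. What is missing is a count, from the measured values and by dose, of patients reaching each level of elevation. This is a worthwhile and cheap reporting improvement. It has no bearing on the primary analysis, the sample size or data collection.

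**What to change.** In Protocol 9.4 and SAP 9.5 and 10.2, keep the existing tables and add one shift table: baseline by worst post-baseline CTCAE v4.03 grade or multiple of ULN, for AST, ALT, ALP, total bilirubin, CPK and creatinine, for each dose and placebo. List it beside Table 14.4.6.2. Amend both documents together, because SAP 12 declares no change from the protocol.

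The rule for the worst value should say:

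- All scheduled post-baseline values available for each test are used. Under Protocol 6.1, AST, ALT, CPK and creatinine have Visits 3 to 6. ALP and total bilirubin are scheduled only at Visits 2, 5 and 6, so they have two scheduled post-baseline values. Protocol 7.5.1 ends chemistry at Visit 5 and should be aligned with 6.1.
- Unscheduled and early-termination values are included; Protocol 6.2.5 and 6.2.6 already provide for chemistry at those visits.
- The Protocol 9.5 censoring of values measured after study drug termination does not remove early-termination laboratory values from this safety table.

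Also state the categories used in Table 14.4.6.2. The cost is a small amount of extra programming on data and a grading scale the trial already has.

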**Every study visit day including Day 1, 85:**

During the study period, electrocardiogram, baPWV, ABI, and image monitoring are performed.

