## **5 SAMPLE SIZE DETERMINATION**

The sample size estimation of this study is using two-sample T-test under one-sided significance level 0.025, power 90%. Based on the Davidson's study, the TG reduction percentage change of 130 mg Fenoribrate from baseline to last visit was 36.6% for subjects who were treated with the study treatment, and the standard deviation was 2.4% and 5.3% for the study treatment and the control treatment. Assuming a drop-out rate of 20%, a sample size of 120 patients (30 patients per arm) were required to provide 96 evaluable patients (24 patients for each group) which indicates an achievement of 80% completion rate.

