## 7.12 Programming Specifications

The summary statistics for continuous variables will be entitled as Number, Mean±SD, Median, Range and 95% C.I. in the table, which represent the number of observations, mean value plus/minus standard deviation, median value of observations, minimum and maximum, lower bound and upper bound of the 95% confidence interval. Range and 95% C.I. are given in parentheses.

Unless otherwise noted, the summary statistics for continuous variables will be printed out to one decimal place except for the standard deviation and confidence interval. The standard deviation and confidence interval will be expressed to 2 decimal places.

In analysis of categorical variable, descriptive statistics will be entitled as frequencies and percentages. All table percentages will be reported with two decimal points unless otherwise specified.

All statistical tests will be conducted under a two-tailed, significance level of 0.05 with related p-value. The p-value will be reported to three decimal places. An asterisk indicates the statistical significance. P-value less than 0.001 will be reported as "< 0.001\*" and p-value greater than 0.999 will be expressed as "> 0.999".

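### SAP 9.5 and Protocol 9.4 offer McNemar's or Fisher's exact test for within-patient changes between visits without a rule for choosing, and Fisher's is not a valid test of paired change

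*SAP*

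**What the plan says.** SAP 9.5 takes the laboratory and ECG results, proposes to "separate subjects into normal and abnormal categories", and then states that "McNemar's test or Fisher's exact test will then be applied to test the changes between each visit". Protocol 9.4 has the same sentence. Neither document gives a rule for choosing between the two tests or says which 2x2 table Fisher's test would be applied to.

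The measurements are repeated on the same patients. For Day 1 and Day 85, SAP 4.1.2 says: "During the study period, electrocardiogram, baPWV, ABI, and image monitoring are performed". It schedules biochemistry at every study visit. SAP 10.2 adds: "The shift tables of laboratory results will also be provided".

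SAP 7.12 sets the level: "All statistical tests will be conducted under a two-tailed, significance level of 0.05", with an asterisk marking significance. SAP 5 gives the arm size: "a sample size of 120 patients (30 patients per arm) were required", with 24 per arm expected to be evaluable after 20% drop-out.

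**The concern.** A change between two visits in one patient is a paired binary outcome. The question is whether more patients move from normal to abnormal than move back, and only the patients who change carry that information. McNemar's test uses exactly those patients. Fisher's exact test assumes two independent classifications or samples, and there are two ways to apply it here:

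- **On the baseline-by-visit shift table.** It then asks whether patients abnormal at one visit tend to be abnormal at the other. That is association, not change.
- **On the two visits' abnormal rates.** It then treats one group of patients as two separate groups and ignores the correlation within patients.

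At stake are the p-values printed beside shifts in measures such as liver enzymes, CPK and ECG. With the choice left open, two analysts following the same sentence could report different results from the same table.

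**Working it through.** The documents state no figure for this test, so there is none to reproduce. The check compares the tests on paired tables at two-sided 0.05.

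**Inputs from the documents.** 30 patients per arm, and 30 x (1 - 0.20) = 24 evaluable (SAP 5); two-sided 0.05 (SAP 7.12).

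**Assumed, not in the documents.** Abnormal rate 10% to 50%; within-patient correlation (phi) from -0.2 to 0.7.

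**Notation.** NN = normal at both visits, NA = normal then abnormal, AN = abnormal then normal, AA = abnormal at both.

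**Formulas.**
- Exact McNemar: two-sided binomial test of NA out of NA + AN with probability 1/2.
- Fisher on the shift table: hypergeometric test on rows (NN, NA) and (AN, AA).
- Fisher on the rates: hypergeometric test of (AN + AA)/n against (NA + AA)/n as if from separate patients.

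**Worked examples, n = 30.**

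| NN, NA, AN, AA | Exact McNemar | Fisher, shift table | Rates compared | Fisher, rates |
|---|---|---|---|---|
| 20, 8, 0, 2 | 0.008 | 0.10 | 2/30 v 10/30 | 0.021 |
| 24, 6, 0, 0 | 0.031 | 1.0 | 0/30 v 6/30 | 0.024 |
| 22, 2, 2, 4 | 1.0 | 0.007 | 6/30 v 6/30 | 1.0 |
| 20, 6, 0, 4 | 0.031 | 0.008 | 4/30 v 10/30 | 0.125 |

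Arithmetic:
- Row 1: McNemar 2 x (1/2)^8 = 0.008. Fisher on the shift table: C(10,2)/C(30,2) = 45/435 = 0.10.
- Row 2: McNemar 2 x (1/2)^6 = 0.031. With nobody abnormal at baseline the shift table has an empty row, so Fisher's p is 1.0 however many patients become abnormal.
- Row 3: the moves balance, 2 against 2, so McNemar gives 1.0. Fisher on the shift table: (4140 + 144 + 1)/593775 = 0.007. It has detected that the same patients tend to be abnormal twice.
- Row 4: McNemar as in row 2. Fisher on the shift table: C(10,4)/C(30,4) = 210/27405 = 0.008, small because of persistence and not because of the shift.

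**False positives with no true change** (20% abnormal at both visits, n = 30):

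| phi | Exact McNemar | Fisher, shift table | Fisher, rates |
|---|---|---|---|
| 0.3 | 1.5% | 29% | 0.7% |
| 0.5 | 0.8% | 65% | 0.2% |
| 0.7 | 0.2% | 90% | 0.01% |

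Over all no-change scenarios run at n = 24 and n = 30, the maximum was 3.0% for McNemar and 4.7% for Fisher on the rates.

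**Power for a true rise from 20% to 40%:**

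| n | phi | Exact McNemar | Fisher, rates |
|---|---|---|---|
| 30 | 0 | 28.3% | 29.8% |
| 30 | 0.3 | 37.6% | 26.0% |
| 30 | 0.5 | 48.6% | 22.2% |
| 30 | 0.6 | 56.2% | 19.7% |
| 24 | 0.5 | 31.9% | 15.8% |

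The two faults belong to different uses. Fisher on the shift table answers another question and can err in either direction. Fisher on the rates keeps its error rate but gives up power as the correlation rises.

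**The case against.** **A benign reading exists.** Elsewhere Fisher's test compares groups (Protocol 9.4 for categorical endpoints; SAP 8.3, 9.2 and 10.1.1). The sentence may be shorthand for McNemar's within arm and Fisher's between arms on the proportion who shift, which would be valid. That is possible, but the sentence speaks of changes between visits and does not mention arms.

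**Nothing shows that Fisher's would be the usual choice.** A reader might infer that small cells at 24 to 30 patients per arm would make it so. The documents do not support this: the small-count rules in Protocol 9.4 and SAP 9.2 concern comparisons between groups, where Fisher's replaces chi-square. No text makes it the fallback for McNemar's, which is named first.

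**The errors depend on the table used.** A reader might also infer that Fisher's both misses shifts and invents them whichever way it is run. It does not. On the rates, the first two examples are detected (0.021 and 0.024) and the third gives 1.0, so all three verdicts from the shift table reverse. The false-signal result belongs to the shift-table use alone.

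**Safety conclusions do not rest on these p-values.** The protocol summary says laboratory data are reported descriptively. SAP 10.2 plans change-from-baseline summaries with confidence intervals, counts against normal ranges, shift tables and flagged listings. SAP 10.3 lists and summarises ECG values, and the planned tables include transition tables for laboratory and ECG results. A shift would be visible whichever test was run. This stands, and it limits the weight of the point. The p-values are also exploratory: many parameters, four arms, 0.05 each.

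What remains is that both documents name, for a paired question, a test that does not answer it, and leave the choice open.

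**Conclusion.** The point holds as a minor one. One of the two tests named in SAP 9.5 and Protocol 9.4 is not valid for within-patient change, and there is no rule for choosing between them.

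The size depends on the use, which the documents do not state. On the shift table, Fisher's can miss a one-way shift (0.10 against 0.008) or flag a table with no net change (0.007 against 1.0). On the rates it did not inflate false positives in any scenario run, but at n = 30 and phi 0.5 its power for a rise from 20% to 40% is 22.2% against 48.6%. At phi = 0 the two are about equal.

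The error rates and powers rest on assumed abnormal rates and correlations. The p-values for the example tables need no such assumption, but the tables are illustrations, not trial data. The effect is limited to the reported safety p-values. The documents do not support a conclusion that a laboratory or ECG safety signal would go unseen.

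**What to change.** Replace the sentence in SAP 9.5 and Protocol 9.4 with wording to this effect:

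*Within each arm, the change in normal/abnormal status from baseline to a later visit will be tested with the exact (binomial) McNemar test, whatever the counts, in patients with both assessments. Fisher's exact test will be used only to compare arms on the proportion of patients newly abnormal after baseline.*

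The exact McNemar test already handles small counts, so no fallback is needed. The cost is one sentence in each document and an option in the software already planned. No new data or visits are required. The change should be made before the SAP is approved and the treatment codes are opened, so that the test is not chosen with the results in view.
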